## 38 **4 Sample Size**

39 A sample size of 160 completers was determined to provide reasonable precision for assessing  
40 safety endpoints and is not based on statistical principles. Up to 200 participants will be enrolled  
41 in the trial so that at least 160 complete the trial. We will aim to enroll approximately 80  
42 participants between 6 and 13 years old and approximately 80 participants ages 14 and older,  
43 with at least 20 participants between 14 and 17 years old. A study wide goal will aim to have at  
44 least 33% of trial completers with a screening HbA1c  $\geq 7.5\%$  and at least 10 completers with a  
45 baseline insulin rate  $>3$  units/hour.

## 46 **5 Endpoints**

### 47 **5.1 Key Safety Endpoints**

- 48 • Severe hypoglycemia
- 49 • Diabetic ketoacidosis
- 50 • Unanticipated adverse device effects (UADE)
- 51 • Other serious adverse events
- 52 • Adverse drug reactions

### 53 **5.2 Secondary Safety Endpoints**

- 54 • All reportable adverse events
- 55 • CGM hypoglycemia outcomes: overall and during postprandial periods for announced  
56 meals, excluding meal challenges described separately below
  - 57 ○ % time  $<54$  mg/dL
  - 58 ○ % time  $<70$  mg/dL
  - 59 ○ Rate of hypoglycemia events, defined as 15 or more consecutive minutes  $<54$  mg/dL  
60 (overall only)

### 61 **5.3 Exploratory Endpoints**

62 *CGM Metrics: overall and during daytime, nighttime, and postprandial periods*

- 63 • % time in range 70-180 mg/dL, % time  $>180$  mg/dL, % time  $>250$  mg/dL, and % time in  
64 range 70-140 mg/dL
- 65 • Mean glucose
- 66 • Glycemic coefficient of variation (CV) and glycemic standard deviation (SD)
- 67 • Rate of hyperglycemia events, defined as 90 or more minutes  $>300$  mg/dL within 120  
68 minutes (overall, daytime, and nighttime only)
- 69 • Postprandial incremental area under the glucose curve (postprandial period only)
- 70 • Peak postprandial glucose (postprandial period only)
- 71 • % time  $<54$  mg/dL, % time  $<70$  mg/dL, and rate of hypoglycemic events, defined as 15  
72 or more consecutive minutes  $<54$  mg/dL (daytime and nighttime only)

73 *HbA1c Metrics*

- 74 • HbA1c change from baseline

75 *Insulin Metrics: overall and during daytime, nighttime, and postprandial periods, calculated per*  
76 *day or per meal as appropriate*

- 77 • Average bolus insulin
- 78 • Average manual bolus insulin
- 79 • Average automated bolus insulin
- 80 • Average basal insulin
- 81 • Average total insulin

82 *System Use: overall*

- 83 • % CGM use
- 84 • % Closed loop use
- 85 • % Time in different operational modes

86 *Patient Reported Outcomes*

- 87 • TRIM-Diabetes (TRIM-D)
  - 88 ○ Total Score
  - 89 ○ Treatment Burden Subscale
  - 90 ○ Daily Life Subscale
  - 91 ○ Diabetes Management Subscale
  - 92 ○ Compliance Subscale
  - 93 ○ Psychological Health Subscale
- 94 • Trim-Diabetes Device (TRIM-DD)
  - 95 ○ Total Score
  - 96 ○ Device Function Subscale
  - 97 ○ Device Bother Subscale
- 98 • Insulin Treatment Satisfaction Question (ITSQ)
  - 99 ○ Total Score
  - 100 ○ Inconvenience Subscale
  - 101 ○ Lifestyle Subscale
  - 102 ○ Hypoglycemic Control Subscale
  - 103 ○ Glycemic Control Subscale
  - 104 ○ Delivery System Subscale

## 105 **6 Calculation of Endpoints**

### 106 **6.1 Safety Endpoints**

107 An event is defined as a severe hypoglycemic event if the event required assistance of another  
108 person due to altered consciousness, and required another person to actively administer  
109 carbohydrate, glucagon, or other resuscitative actions.

110 An event is classified as a DKA event if the following occur:

- 111 • Symptoms such as polyuria, polydipsia, nausea, or vomiting;
- 112 • Serum ketones >1.5 mmol/L or large/moderate urine ketones;
- 113 • Either arterial blood pH <7.24 or serum bicarbonate (or CO2) <15; and
- 114 • Treatment provided at a health care facility

115

116 For each of the endpoints listed in Section 5.1, the total number of events for each participant  
117 and the event rate per 100 person years will be calculated. Event rates will be calculated as the  
118 total number of events occurring after the start of the treatment period divided by the number of  
119 person years the participant was active in the study. The person years will be calculated as the  
120 number of days between the start of treatment period and either the 13-week visit date or drop  
121 out date divided by 365.25.

122 The proportion of participants with at least 1 or more severe hypoglycemia and DKA events will  
123 be compared with published T1D Exchange data matched by age group (<18 years and ≥18  
124 years) (Table 1). An overall proportion will also be compared with the expected proportions  
125 from the T1D Exchange population using weights derived from the age groups. Study endpoint  
126 will be met if severe hypoglycemia and DKA event rates are not significantly higher during  
127 follow-up compared with T1D Exchange frequency.

128 A sensitivity analyses will restrict to severe hypoglycemic events occurring during the treatment  
129 period which resulted in a seizure or loss of consciousness, and DKA events which resulted in  
130 inpatient hospitalization or prolongation of existing hospitalization.

131 Adverse events occurring in the treatment phase during periods where Humalog is used will be  
132 reported separately.

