### 685 **6.2.3 Hypoglycemic Events**

686 Hypoglycemia not associated with an Adverse Device Effect or discontinuation of the study device or  
687 study drug is only reportable as an adverse event when one of the following criteria is met:

- 688 • a hypoglycemic event occurred meeting the following definition of severe hypoglycemia: the  
689 event required assistance of another person due to altered consciousness, and required another  
690 person to actively administer carbohydrate, glucagon, or other resuscitative actions. This means  
691 that the participant was impaired cognitively to the point that he/she was unable to treat  
692 himself/herself, was unable to verbalize his/ her needs, was incoherent, disoriented, and/or  
693 combative, or experienced seizure or loss of consciousness. These episodes may be associated  
694 with sufficient neuroglycopenia to induce seizure or loss of consciousness. If glucose  
695 measurements are not available during such an event, neurological recovery attributable to the  
696 restoration of glucose to normal is considered sufficient evidence that the event was induced by  
697 a low glucose concentration.
- 698 • evaluation or treatment was obtained at a health care provider facility for an acute event involving  
699 hypoglycemia, or the participant contacted the site and received guidance following the  
700 occurrence of an acute event involving hypoglycemia

701 When a severe hypoglycemia event occurs (as defined above), a Hypoglycemia Form should be  
702 completed in addition to the Adverse Event Form. Severe hypoglycemia events should be considered  
703 to be serious adverse events with respect to reporting requirements. When a severe hypoglycemia event  
704 occurs during use of a study device, it generally will be considered to be unrelated to the device (per  
705 section 6.2.6) if the device functioned as intended and there does not appear to be a flaw in how the  
706 device is intended to function.

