## 274 **8 Statistical Analyses**

### 275 **8.1 Key Safety Analyses**

276 The total number of events, number and proportion of participants who experienced at least one  
277 event during the treatment period and the rate of events per 100 person years will be tabulated  
278 for each outcome listed in Section 5.1. The proportion of SH and DKA events will be compared  
279 to proportions of events occurring in a similar time frame among participants enrolled in the T1D  
280 exchange. These proportions have been previously published [2].

281 Barnard's exact test will be used to test the difference in proportions. A two-sided p-value testing  
282 the null hypothesis of no difference in proportions will be reported. For unanticipated adverse  
283 device effects, adverse drug reactions, and serious adverse events, the total number, number and  
284 proportion of participants who experienced at least one event during the treatment period and the  
285 rate of events per 100 person years will be tabulated.

286 All analyses described in this section will be repeated restricting to only severe hypoglycemic  
287 events that were associated with a seizure or loss of consciousness. Summary statistics will be  
288 reported for key safety outcomes by age group (6-13, 14-17, 18-25, 26-49,  $\geq 50$ ).

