**Most Recent HbA1c**

<7.0% (<53 mmol/mol)	96	0	174	1 (1%)	257	2 (1%)	575	2 (<1%)	498	3 (1%)
7.0-<7.5% (53-<58 mmol/mol)	148	1 (1%)	268	3 (1%)	283	3 (1%)	395	2 (1%)	372	2 (1%)
7.5-<8.0% (58-<64 mmol/mol)	214	3 (1%)	410	2 (1%)	341	5 (1%)	357	2 (1%)	375	0
8.0-<9.0% (64-<75 mmol/mol)	420	5 (1%)	866	18 (2%)	596	9 (2%)	398	9 (2%)	397	8 (2%)
≥9.0% (≥75 mmol/mol)	380	20 (5%)	1370	83 (6%)	888	74 (8%)	265	25 (9%)	184	5 (3%)

461  
462

a – A severe hypoglycemic event required loss of consciousness or seizure.  
b – A diabetic ketoacidosis event diagnosed by a doctor and required an overnight hospitalization.

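### The registry pass/fail comparison uses different event definitions on its two sides: wider for severe hypoglycemia in the trial, of uncertain direction for DKA, and the closest matched version has no role in the decision

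*SAP*

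**What the plan says.** SAP 6.1 defines a severe hypoglycemic event as one needing help from another "person due to altered consciousness, and required another person to actively administer" carbohydrate, glucagon or other resuscitation. Protocol 6.2.3 uses the same core wording ("event required assistance of another person due to altered consciousness, and required another" person to treat). It lists incoherence, disorientation and combativeness as alternatives to seizure or loss of consciousness.

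For DKA, SAP 6.1 requires symptoms, a ketone criterion, a pH or bicarbonate criterion and "Treatment provided at a health care facility". Protocol 6.2.4 has the same structure.

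The proportion of participants with at least one event is compared with Table 1 in SAP 15 by Barnard's exact test (SAP 8.1, Protocol 8.6.1). The study endpoint "will be met if severe hypoglycemia and DKA event rates are not significantly higher during" follow-up than in the registry. The footnotes to Table 1 give the registry's definitions: "A severe hypoglycemic event required loss of consciousness or seizure", and "A diabetic ketoacidosis event diagnosed by a doctor and required an overnight hospitalization".

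Directly after the rule, SAP 6.1 adds: "A sensitivity analyses will restrict to severe hypoglycemic events occurring during the treatment" period that led to seizure or loss of consciousness, and DKA that led to or prolonged an inpatient stay. SAP 8.1 then says: "All analyses described in this section will be repeated restricting to only severe hypoglycemic" events with seizure or loss of consciousness. It does not mention DKA.

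**The concern.** The rule that decides whether the study met its endpoint sets one kind of event in the trial against another kind in the registry. An assisted hypoglycemic event without seizure or unconsciousness counts in the trial and not in the benchmark. A system exactly as safe as the registry on the registry's own definition could therefore be declared significantly worse. The analysis that would show this is planned, but nothing in the rule refers to it. For DKA the definitions also differ, so neither a pass nor a fail on that component is a like-for-like statement.

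**Working it through.** **1. The definitions side by side**

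| | Trial (SAP 6.1; Protocol 6.2.3, 6.2.4) | Registry (SAP 15, footnotes) | Trial relative to registry |
|---|---|---|---|
| Severe hypoglycemia | Assisted, altered consciousness | Seizure or loss of consciousness | Wider |
| DKA, setting | Treated at any health care facility | Overnight hospitalization | Wider |
| DKA, diagnosis | Symptoms, ketones and pH or bicarbonate all required | Doctor's diagnosis; no biochemical criteria listed | Narrower |

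So the direction is clear for severe hypoglycemia (SH) and not for DKA. Within DKA, SAP 6.1 also gives an arterial pH cut-off of 7.24, where Protocol 6.2.4 gives 7.30 arterial or 7.24 venous. The two passages need to be reconciled.

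**2. Table 1 reproduced (overall row)**

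- SH: 62/1313, 155/3183, 138/2445, 157/2143, 189/1976 = 4.72, 4.87, 5.64, 7.33, 9.56%, matching the printed 5, 5, 6, 7, 10%.
- DKA: 31/1313, 113/3183, 96/2445, 43/2143, 22/1976 = 2.36, 3.55, 3.93, 2.01, 1.11%, matching the printed 2, 4, 4, 2, 1%.

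**3. Age-weighted SH benchmark**

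The sample-size section aims for about 80 participants aged 6 to 13 and at least 20 aged 14 to 17, out of 160. I assume a 100:60 split below 18 and 18 or over.

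- Below 18: (62+155)/(1313+3183) = 217/4496 = 4.83%.
- 18 and over: (138+157+189)/(2445+2143+1976) = 484/6564 = 7.37%.
- Weighted: (100 × 4.83 + 60 × 7.37)/160 = 5.78%.

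**4. Where significantly higher begins**

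Assumptions: 180 treated (between the 160 completers and the 200 maximum), two-sided 0.05 (the SAP states no level for these tests), and a pooled two-proportion z-test against 4496 + 6564 = 11,060 registry participants as an approximation to Barnard's test.

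- 17 participants: 17/180 = 9.44%. Pooled proportion = (17 + 0.0578 × 11,060)/(180 + 11,060) = 5.84%. z = (0.0944 − 0.0578)/√[0.0584 × 0.9416 × (1/180 + 1/11,060)] = 2.08.
- 16 participants: z = 1.76.

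The threshold is 17. At 160 treated, a Barnard-type exact calculation gives 16 (p = 0.024; 15 gives 0.054).

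**5. Chance of a false finding for SH**

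Let p be the true risk on the registry's definition. Let k be the capture ratio: participants with a trial-defined event divided by participants with a registry-defined event. The chance is P(X ≥ 17) with X binomial(180, k × p). The documents do not give k; the range shown is 1 to 2.

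The second row of the table takes p from the registry's CGM users: 29/998 = 2.91% below 18, 92/1685 = 5.46% at 18 and over, weighted 3.86%. The benchmark and threshold are unchanged.

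| True matched risk p | k = 1 | k = 1.5 | k = 2 |
|---|---|---|---|
| 5.78% (overall row) | 3% | 39% | 84% |
| 3.86% (CGM-user row) | 0.07% | 3% | 23% |

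With 160 treated and a threshold of 16, the first row becomes 2.4%, 31% and 77%.

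**6. DKA**

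No comparable figure is offered. The calculation would need k to be at least 1, and step 1 shows that it could lie on either side of 1.

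**The case against.** **The restricted analysis is already prespecified for both events, and the registry definitions are printed.** This stands. A reader of SAP 8.1 alone might infer that no matched DKA analysis exists, but SAP 6.1 plans one. What remains is that neither section gives the restricted result any part in the decision, and that 8.1 does not carry the DKA restriction through.

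**The mismatch is conservative.** A reader might infer that it helps the sponsor pass. For SH it does the opposite: the wider trial definition can cause a false fail, not a false pass. A stricter test is defensible in a safety study, but a fail under it could not be interpreted. For DKA, conservatism cannot be claimed. Nor can the reverse inference, that the trial's DKA definition can only add cases: an overnight, doctor-diagnosed case that misses the biochemical criteria counts in the registry and not in the trial.

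**The trial population should have lower risk than the registry overall row.** Participants are established closed-loop users, and people with more than one SH or DKA episode in the past 6 months are excluded. This is fair, and is why the CGM-user row is shown.

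**The suspension rules would act first.** Protocol 6.6.2 suspends closed-loop use for a root cause analysis at 5 SH cases study-wide, or suspends the pediatric cohort at 3. Counts near 17 are therefore less likely. But use may resume, and the rule does not make the comparison like-for-like.

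**Conclusion.** The point holds. The endpoint rule compares unlike events: biased towards a false finding of significantly higher for SH, and in an unknown direction for DKA. The nearest matched analysis is planned but does not decide anything, and SAP 8.1 omits its DKA part.

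A reader might infer from the 39% and 84% that a false fail is likely. The documents do not support that. Those figures rest on an assumed 180 treated, a 100:60 age split, a two-sided 0.05 level, an assumed capture ratio and a true matched risk equal to the registry overall row. With the CGM-user risk the same ratios give 3% and 23%. The definitional mismatch is established by the text; its numerical effect is an illustration. It merits a change because it bears on the study's deciding statement.

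**What to change.** - In SAP 6.1 and 8.1, and in Protocol 8.6.1 and the synopsis endpoint, tie the endpoint rule to the definition-matched comparison: SH with seizure or loss of consciousness, and DKA with overnight or inpatient hospitalization.
- Add DKA to the restricted repeat in SAP 8.1, so that it agrees with 6.1.
- State that the DKA match is approximate: an inpatient stay is not quite an overnight one, and the trial's biochemical criteria have no counterpart in the registry footnote.
- Keep the full protocol definitions as key safety endpoints, with counts, proportions, rates and a supportive registry comparison.

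**Cost.** No new data are needed, because the sensitivity analysis already requires seizure, unconsciousness and hospitalization to be recorded. It is more than an SAP edit: the synopsis and Protocol 8.4 and 8.6.1 tie the comparison to the wider definitions, so the protocol must change too. Fewer events enter the deciding comparison and, for SH, the endpoint becomes easier to meet. Both versions should therefore be reported side by side.

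**Timing.** SAP version 4.0 is dated after enrollment and follow-up were complete. If outcome data are already known, date the change and present the matched result beside the planned one, not in its place.

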### 707 **6.2.4 Hyperglycemic/Ketotic Events**

708 Hyperglycemia not associated with an Adverse Device Effect or discontinuation of the study device or  
709 study drug is only reportable as an adverse event when one of the following criteria is met:

- 710 • the event involved DKA, as defined by the Diabetes Control and Complications Trial (DCCT)  
711 and described below
- 712 • evaluation or treatment was obtained at a health care provider facility for an acute event involving  
713 hyperglycemia or ketosis, or the participant contacted the site and received guidance on how to  
714 manage the hyperglycemia/ketosis
- 715 • blood ketone level  $\geq 1.0$  mmol/L, even if there was no communication with a health care provider  
716 at the time of the event

717 Hyperglycemic events are classified as DKA if the following are present:

- 718 • Symptoms such as polyuria, polydipsia, nausea, or vomiting;
- 719 • Serum ketones  $>1.5$  mmol/L or large/moderate urine ketones;
- 720 • Either arterial blood pH  $<7.30$  or venous pH  $<7.24$  or serum bicarbonate (or CO2)  $<15$ ; and
- 721 • Treatment provided in a health care facility

722 When a hyperglycemia/ketotic event qualifies as an SAE as defined in section 6.2.1, a Hyperglycemia/  
723 DKA Form should be completed in addition to the Adverse Event Form. Events meeting DKA criteria  
724 should be considered to be serious adverse events with respect to reporting requirements. Hyperglycemia  
725 events not meeting criteria for DKA generally will not be considered as serious adverse events unless one  
726 of the SAE criteria in section 6.2.1 is met.

727 When a hyperglycemia/DKA event occurs during use of a study device, it generally will be considered to  
728 be unrelated to the device (per section 6.2.6) if the device functioned as intended and there does not  
729 appear to be a flaw in how the device is intended to function.

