### 778 **6.2.9 Coding of Adverse Events**

779 Adverse events will be coded using the MedDRA dictionary. To facilitate coding, the site will enter a  
780 preliminary MedDRA code which the Medical Monitor may accept or change (the Medical Monitor's  
781 MedDRA coding will be used for all reporting). The Medical Monitor will review the investigator's  
782 assessment of causality and may agree or disagree. Both the investigator's and Medical Monitor's  
783 assessments will be recorded. The Medical Monitor will have the final say in determining the causality  
784 as well as whether an event is classified as a serious adverse event and/or an unanticipated adverse device  
785 effect.

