#### Key Safety Endpoints

947

- 948 • Severe hypoglycemia as defined in section 6.2.3
- 949 • Diabetic ketoacidosis as defined in section 6.2.4
- 950 • Unanticipated adverse device effects
- 951 • Other serious adverse events
- 952 • Adverse drug reactions

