## Contents

1	Consistency of Statistical Analysis Plan with Protocol .....	6
2	Study Overview .....	6
3	Statistical Hypothesis.....	6
4	Sample Size.....	7
5	Endpoints .....	7
5.1	Key Safety Endpoints.....	7
5.2	Secondary Safety Endpoints.....	7
5.3	Exploratory Endpoints.....	7
6	Calculation of Endpoints .....	8
6.1	Safety Endpoints .....	8
6.2	CGM Endpoints.....	9
6.2.1	Details for Postprandial Periods Not Associated with Meal Challenges .....	9
6.2.2	CGM Use .....	10
6.2.3	CGM Endpoints Following Meal and Exercise Challenges .....	10
6.3	Insulin Endpoints.....	11
6.3.1	Insulin Endpoints during Post-Meal Periods Not Associated with Meal Challenges 11	
6.3.2	Insulin Endpoints Following Meal and Exercise Challenges .....	12
6.4	Closed Loop Use .....	12
6.5	Patient Reported Outcomes .....	12
6.5.1	TRIM-D and TRIM-DD .....	12
6.5.2	ITSQ.....	12
7	Analyses Cohorts .....	12
7.1	Analysis Windows.....	12
8	Statistical Analyses .....	13
8.1	Key Safety Analyses .....	13
8.2	Secondary Safety Analyses .....	13
8.3	Exploratory Analyses .....	14
8.4	Meal and Exercise Challenges .....	14
8.5	Protocol Adherence and Retention Analysis.....	14
9	Baseline Descriptive Statistics.....	15

10	Additional Analyses.....	15
10.1	Device Issues .....	15
10.2	Infusion Site Reactions.....	15
10.3	Open-Loop Basal Rates .....	16
11	Subgroup Analyses .....	16
12	Trial Level Safety Review .....	17
13	Multiple Comparisons.....	17
14	References.....	18
15	T1D Exchange Published Table .....	19

1 **1 Consistency of Statistical Analysis Plan with Protocol**

2 All analyses listed in this document are consistent with study protocol (version indicated on the  
3 version history table).

4 **2 Study Overview**

5 The Tandem t:slim X2 pump with Control-IQ technology is a closed loop automated insulin  
6 delivery system approved by FDA. Lyumjev™ is a rapid acting human insulin analog that has  
7 been shown to improve glycemic control in adults with diabetes. This document outlines the  
8 statistical analyses to be performed for a clinical trial evaluating the impact of Lyumjev used  
9 with the Control-IQ system.

10 The study population includes individuals ages 6 to <81 years old with a diagnosis of type 1  
11 diabetes for at least 1 year who are currently using Control-IQ technology. This is a prospective,  
12 single arm study.

13 **3 Statistical Hypothesis**

14 The primary objective of the study is assessment of safety. Severe hypoglycemia and diabetic  

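### SAP 6.1 defines DKA more narrowly than the protocol definition assigned to the key safety endpoint; if applied, it can only lower the DKA count

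*SAP*

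**What the plan says.** Protocol 8.4 lists the key safety endpoint as "Diabetic ketoacidosis as defined in section 6.2.4". Protocol 6.2.4 gives the acidosis criterion as "Either arterial blood pH $<7.30$ or venous pH $<7.24$ or serum bicarbonate" (or CO2) below 15, together with symptoms, ketones and treatment in a health care facility.

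SAP 6.1, in the chapter on calculating endpoints, gives the criterion as "Either arterial blood pH <7.24 or serum bicarbonate" (or CO2) below 15. Its other three DKA requirements match the protocol in substance.

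SAP 1 states: "All analyses listed in this document are consistent with study protocol". The SAP version history, through version 4.0, lists no change to the DKA definition, and every SAP version cites the same protocol version, 4.0.

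The DKA count carries a decision. SAP 6.1 says the study endpoint "will be met if severe hypoglycemia and DKA event rates are not significantly higher during" follow-up than in the T1D Exchange registry. SAP 8.1 says that Barnard's "exact test will be used to test the difference in proportions", with a two-sided p-value.

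**The concern.** The SAP attaches the protocol's venous cut-off to arterial blood. It drops both the arterial 7.30 cut-off and the venous route. A programmer who follows SAP 6.1 and an adjudicator who follows protocol 6.2.4 could therefore classify the same event differently.

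The difference runs in one direction. An event that is DKA, and so an SAE, under protocol 6.2.4 could be left out of the DKA count and out of the registry test. It would not vanish, because it could still be tabulated among other serious adverse events. That category, however, is not tested against the registry and plays no part in the endpoint-met rule. In a single-arm safety study meant to support labeling, a reader of the DKA table needs to know which rule produced it.

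**Working it through.** **1. The two rules side by side**

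| Criterion | Protocol 6.2.4 | SAP 6.1 |
|---|---|---|
| Arterial pH | <7.30 | <7.24 |
| Venous pH | <7.24 | not accepted |
| Bicarbonate/CO2 | <15 | <15 |
| Symptoms, ketones, treatment setting | same in substance | same in substance |

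**2. Direction.** Arterial pH <7.24 implies arterial pH <7.30, and the bicarbonate limb is identical, so every event that meets the SAP rule meets the protocol rule. An enumeration over arterial pH (missing or 6.80 to 7.45), venous pH (same) and bicarbonate (missing or 3 to 28) agrees: 98,088 combinations met both rules, 17,250 the protocol rule only, 0 the SAP rule only, and 5,865 neither. These are grid cells, not event frequencies.

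**3. Events lost under the SAP text.** These have bicarbonate/CO2 of 15 or more, or not measured, and either
- arterial pH from 7.24 to below 7.30, or
- venous pH below 7.24 with arterial pH not measured or at least 7.24.

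The documents do not allow their number to be estimated. The registry footnote (SAP 15, Table 1, note b) defines an event as "diagnosed by a doctor and required an overnight hospitalization", with no pH criterion, so it gives no guide to the share of events in these bands.

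**4. Effect of one lost participant.** If a participant's only DKA event is lost, the proportion falls by 1/160 = 0.63 percentage points.

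**5. Registry rates (SAP Table 1) and expected participants with DKA per 160**

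| Reference | Count | Rate | Expected in 160 |
|---|---|---|---|
| All: 31+113+96+43+22 | 305/11,060 | 2.76% | 4.4 |
| Pump users: 12+49+44+24+14 | 143/7,377 | 1.94% | 3.1 |
| CGM users: 4+9+9+5+1 | 28/2,683 | 1.04% | 1.7 |

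**6. Where the verdict turns.** The test is two-sided Barnard with the pooled statistic. The SAP states no alpha for it, so 0.05 is assumed. The p-value is maximized over about 8,000 values of the nuisance proportion.

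| Comparison | Not significant | Significant |
|---|---|---|
| n=160 vs 305/11,060 | 10 (p=0.054) | 11 (p=0.045) |
| n=200 vs 305/11,060 | 12 (p=0.056) | 13 (p=0.035) |
| <18 years, n=100 vs 144/4,496 | 8 (p=0.055) | 9 (p=0.030) |
| ≥18 years, n=60 vs 161/6,564 | 5 (p=0.052) | 6 (p=0.034) |

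The age-group sizes are assumptions. The 100 is the sum of the minimums of 80 aged 6 to <14 and 20 aged 14 to <18. The 60 is the 80 aged 14 and over less those 20; no adult minimum is stated.

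The software matters. With scipy's coarse nuisance sampling the overall verdict at n=160 turns earlier, between 8 (p=0.091) and 9 (p=0.029).

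**7. Chance of reaching the turning point at n=160** (binomial, true rate equal to the reference rate)

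| Reference rate | P(9 or more) | P(11 or more) |
|---|---|---|
| All, 2.76% | 0.034 | 0.005 |
| Pump users, 1.94% | 0.004 | 0.0003 |
| CGM users, 1.04% | 0.00005 | 0.000001 |

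For the discrepancy to change the verdict, the true count must be at or just above the threshold, and enough of those participants must fall in the bands of step 3.

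**The case against.** The best reply is that the SAP sentence may never operate. Sites report DKA under protocol 6.2.4, the Medical Monitor reviews every adverse event form, and protocol 6.2.9 says the Medical Monitor's "MedDRA coding will be used for all reporting". No section describes re-deriving DKA from pH values. On that route the numerical effect is nil. That is a fair account of what may happen, but 6.2.9 covers coding, causality and SAE/UADE status. Neither document names that classification as the source of the DKA table, and SAP 6.1 states its own rule for when an event counts as DKA.

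A second reply is that this is a slip: the omitted words are those between two occurrences of the same symbol string. That is plausible as a cause. The SAP line is grammatical and complete as it stands, so loss in reading the PDF is less likely, though a look at the page would settle it. A slip in an operative definition still needs correcting.

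Third, the practical stakes are small. Protocol 6.6.2 suspends closed-loop use for root cause analysis at 5 hyperglycemic/ketotic SAEs across the study, and suspends the pediatric cohort at 3. The overall and under-18 turning points lie above those counts, and the binomial figures ignore the suspension. The SAP's overall comparison also uses age weights: at a 100/60 split the expected rate is (100 × 3.20% + 60 × 2.45%)/160 = 2.92%, not 2.76%. These points stand. They bear on the chance of a changed verdict, not on the contradiction.

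**Conclusion.** The concern holds. The current protocol and the current SAP give the key DKA endpoint two definitions, and the SAP's is a strict subset of the protocol's. If the SAP wording is applied, the DKA count can fall or stay the same but cannot rise, and a lower count favors meeting the endpoint. The number of events at risk is not derivable from the documents and may be zero.

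A change in the overall verdict is unlikely. At n=160, alpha 0.05 and the crude registry rate, the chance of reaching the turning point is 0.034 (coarse nuisance sampling) or 0.005 (full search), before asking whether any event falls in the lost pH bands. The direction and the contradiction rest on the texts alone; the thresholds and probabilities rest on the assumed alpha, group sizes and rates. This should be fixed because the endpoint feeds a decision rule, not because a large numerical effect is expected.

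**What to change.** Reconcile SAP 6.1 with protocol 6.2.4 by using, for the endpoint, the definition that protocol 8.4 cross-references. Add one sentence saying whether the Medical Monitor's classification is the source of the DKA count. Derive every DKA table, the registry comparison and the hospitalization sensitivity analysis from that single definition, and check any program already written to the SAP text.

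The cost is one line of SAP wording, one sentence and a program check, with no new data. Relative to the SAP text, the DKA count can only stay the same or rise. The change is a matter of consistency between the documents and does not judge which pH threshold is clinically right.
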